799 are assessed every 6 months from baseline to 5 years of therapy. Thus, analyses of bone biopsy endpoints
800 involve both within-arm and between-arm comparisons at the 3 times, while all other analyses will utilize
801 standard repeated measures methods for longitudinal data.

802 These analyses will initially include all randomized subjects who remain evaluable for the endpoints,
803 including those eligible out of the subjects currently on conventional therapy plus the 36 newly enrolled
804 subjects. However, if covariate adjustment in analyses described below indicates that there are differences
805 between these strata, then the 3 strata will be analyzed separately. The subjects who were on HPTH under
806 the previous version of the protocol will be analyzed separately using similar analysis methods,
807 recognizing the limitations of the small sample size (≤ 8). Any subject who enters menopause prior to the
808 second bone biopsy will remain in the study and will undergo the second biopsy; however, the results will
809 be reported separately and not included in the data analyses of the randomized groups. It is felt that
810 reviewing the results from a menopausal woman anecdotally may give insight into possible treatment
811 effects in a menopausal sub-population. Data will be summarized graphically and in tabular form using
812 standard descriptive statistics for categorical and continuous measures, with appropriate consideration of
813 underlying distributional assumptions. All tests of significance will be two-tailed at the 0.05 level.

814 For the bone biopsy endpoints, paired t-tests will be used to test the hypotheses that the 1, 2, and 4-year
815 changes from baseline are significantly different from zero. One-way analysis of variance (ANOVA) will
816 be used to compare these differences to each other, with protected individual linear contrasts performed if

817 the overall F-test is significant. The effects of selected baseline covariates, including gender and
818 menopausal status, will be assessed using analysis of covariance (ANCOVA) in a sensitivity analysis.
819 Exploratory graphical methods will also be used to assess distributional assumptions and potential
820 differences in responses between the strata. Log-transformation of raw data or non-parametric test
821 alternatives may be considered if indicated by these exploratory analyses.

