7.4 Analysis Methods

All study endpoints used in analyses will be summarized in tables. Continuous endpoints will be summarized over time using n, mean \pm se, median, min, max. Endpoints requiring log-transformation will also be summarized over time using geometric means with their 95% confidence limits. Ordinal endpoints will be summarized using medians, min, max, and their 10th and 90th percentiles. Categorical endpoints will be summarized using number and percent in each category.

All efficacy analyses related to the bone biopsies will be performed on the Bone Biopsy Population. All efficacy analyses other than the bone biopsy related endpoints will be performed on the Secondary Efficacy Population.

For subjects who enter menopause during the study, any of their efficacy endpoints collected during or post-menopause will be excluded from the efficacy analyses, and will have such endpoints reported separately in the subject listings.

Unless otherwise stated, all statistical inference will be based on an alpha level of 0.05 with adjustments for multiple comparisons when needed as described below. Analyses will be made using SAS (SAS Institute, Cary, North Carolina), version 9.4 or later.

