7.4.1 Primary Efficacy Analyses

Separate primary analyses will be performed for each of the eight primary bone structure and bone remodeling biopsy endpoints listed in section 7.2.1. Since the study was terminated early and is thus under-powered, no corrections for multiplicity will be made in the analyses of the 8 primary efficacy endpoints. For each of these primary bone biopsy endpoints, the primary analysis will test for differences with respect to the time of the biopsy (baseline, 1, 2, and 4 year). These endpoints will be analyzed using repeated measures mixed models with the bone biopsy endpoint as the dependent variable, the baseline value of the bone biopsy endpoint and study cohort as covariates, biopsy time (baseline, 1 year, 2 year, and 4 year) as the repeated measure, and subject as the random variable. The repeated measures will include a time-dependent covariate to adjust the baseline biopsy of Cohort 2 for the time delay between the baseline biopsy and the start of hPTH treatment. This covariate will adjust Cohort 2 for any possible further progression of disease occurring between the baseline biopsy measures and the start of hPTH therapy. An indicator variable in the statistical model will set the effects of this time-dependent covariate to zero for Cohort 3 and for the post-baseline biopsies of Cohort 2.

Pairwise contrasts between the bone biopsy times will be performed within the repeated measures analyses to compare the effects of the biopsy times on the bone biopsy endpoints. Because the sample size for 2-year and 4-year biopsies are reduced in size due to withdrawal and the early termination of the study, the 2-, and 4-year biopsies may be combined into one group provided their effects are qualitatively similar (i.e. the estimates of their effects are in the same direction). If the 2- and 4-year biopsies are qualitatively different then the 4-year biopsies may be dropped from the analysis due to its small sample size. The post hoc pairwise comparisons among the

biopsy time-points will be corrected for multiple comparisons using Fisher's protected LSD with Bonferroni corrections when the overall effect of biopsy year is not statistically significant.

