Parameters derived from the back-scattered electron imaging of the bone biopsies include the spectral calcium mean, peak, width, low, and high. These spectral calcium parameters will be analyzed separately using repeated measures mixed models with the spectral calcium parameter as the dependent variable, the baseline value of the biopsy endpoint and study cohort as covariates, biopsy time (baseline, 1 year, 2 year, and 4 year) as the repeated measure, and subject as the random variable. Because there are only a few subjects with the 4 year biopsy, the 2 and 4 year biopsies may be collapsed into one biopsy group for analysis purposes if the 2 and 4 year biopsies appear to have similar effect sizes and variances. If the 2- and 4-year biopsies are qualitatively different then the 4-year biopsy endpoints may be dropped from the analysis due to their small sample sizes. Pairwise contrasts will be performed within the repeated measures analyses to compare the effects of the biopsy times on the bone biopsy endpoints.

Since these spectral calcium parameters are secondary endpoints, these analyses are considered more exploratory and thus no adjustments will be made for performing multiple secondary analyses. However, post hoc pairwise comparisons within each repeated measures analysis will be controlled for multiple comparisons using Fisher's protected LSD followed by Bonferroni correction if the overall effect is not significant.

Results will be summarized in a table. The effects of hPTH treatment on the spectral calcium endpoint will be illustrated in figures of the mean \pm se (or geometric means with 95% confidence limits) over biopsy time.

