7.4.2.4 Repeated measures analyses of the non-biopsy secondary endpoints

The secondary non-biopsy secondary endpoints are listed in section 7.2.2.

Unlike the biopsy endpoints, the secondary non-biopsy secondary endpoints had measurements at baseline and then every 6 months over the 5 years of the study as compared to biopsies at baseline, 1, 2, and 4 years of hPTH treatment. As a complication, subjects were on hPTH therapy for various lengths of time due to study withdrawal and early study termination. Thus, the effects of study month are not the same for each subject with some subjects on hPTH therapy and some

subjects off hPTH therapy for the later study months. Thus, the 6-month time-points will be reduced to the following experimental time-points: baseline visit, 6-month study visit, end of hPTH therapy, and post-hPTH follow-up visit.

The effect of hPTH therapy over the experimental time-points (baseline, 6-month study visit, last hPTH treatment, and post-hPTH follow-up) on each of the non-biopsy endpoint parameters will be analyzed using repeated measures mixed models with the non-biopsy endpoint as the dependent variable, the baseline value of the non-biopsy endpoint, and study cohort as covariates, the experimental time-point as the repeated measure, and subject as the random factor. If dose is found to improve model fits in the bone-biopsy repeated measures analyses (section 7.4.2.1) then the effect of dose will be added as a covariate to these secondary repeated measures. Pairwise post hoc comparisons will be made to test for endpoints differences among the experimental time-points (baseline, 6-month study visit, last hPTH treatment, and post-hPTH follow-up). The significance of these post hoc pairwise comparisons will be corrected for multiple comparisons using Fisher's protected LSD. When the repeated measures overall effects of study time-point are not significant, Bonferroni corrections will be used to adjust the pairwise contrasts for multiplicity.

Residual analysis will be used to confirm that repeated measures model assumptions are reasonable. Log-transformations of the bone biopsy endpoints will be made if indicated by the residual analysis. The repeated measures will be fit using both a compound symmetry and an unstructured covariance structure. The better covariance structure will be selected as the model with the better Schwarz- Bayesian criterion.

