9. CHANGES TO THE ANALYSES PLANNED IN THE PROTOCOL

The study was discontinued early, due to pharmacy issues. Upon termination of new enrollment in June of 2015, subjects began to be slowly weaned off of hPTH. Of the 32 planned, newly enrolled subjects, only 19 were actually enrolled and treated and of these, 8 subjects provided their on-treatment biopsy. This early termination provides less power to detect significant differences in endpoints. We will evaluate the possibility of combining the 2- and 4- year biopsy groups to address this issue (see section 7.4.1 for details).

The primary bone biopsy endpoints have changed. The original primary endpoints included: 1) mineralized perimeter; 2) bone formation rate; 3) cortical width; 4) cortical area; 5) osteoid width; 6) osteoid perimeter; and 7) mineral apposition rate. These primary bone biopsy endpoints have been replaced with the eight primary endpoints listed in section 7.2.1. In the analysis of the pilot study of the first 5 patients as well as other relevant pilot studies, we learned that these are the more informative indices.

The primary and secondary analyses will be performed using repeated measures mixed models rather than the paired t-tests, ANOVA, and ANCOVA analyses as stated in the protocol.

Although the protocol specifies imputation analyses for all secondary endpoints collected every 6 months over the 5-year study period, for purposes of efficiency the sensitivity analyses using multiple imputation (Proc MI in SAS) of missing values will be initially limited to the primary efficacy bone biopsy endpoints. After reviewing patterns of missing-ness in the secondary endpoints, additional sensitivity analyses involving multiple imputations may be performed at the request of the PI.

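### With four time levels, protected LSD leaves the pairwise contrasts unadjusted once the overall test rejects, yet the SAP describes them as corrected or controlled

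*SAP*

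**What the plan says.** SAP 7.4 sets the general rule: "all statistical inference will be based on an alpha level of 0.05 with adjustments for multiple comparisons when needed as described below". SAP 7.4.1 then fits one time factor with baseline as a level beside years 1, 2 and 4. It describes the pairwise comparisons as corrected by Fisher's "protected LSD with Bonferroni corrections when the overall effect of biopsy year is not statistically significant". No adjustment is given for the case where the overall test is significant. The waiver of multiplicity correction in that section concerns the eight primary endpoints, not the contrasts within one endpoint.

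Two secondary sections use the same rule. SAP 7.4.2.3: "post hoc pairwise comparisons within each repeated measures analysis will be controlled for multiple comparisons using" protected LSD, with Bonferroni if the overall effect is not significant. SAP 7.4.2.4 has four time-points ("baseline visit, 6-month study visit, end of hPTH therapy, and post-hPTH follow-up visit") and says: "When the repeated measures overall effects of study time-point are not significant, Bonferroni corrections will be used to adjust the pairwise contrasts for multiplicity". SAP section 10 defines experimental time by three visits and omits the 6-month visit.

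SAP 7.4.1 offers two routes to three levels. The 2- and "4-year biopsies may be combined into one group provided their effects are qualitatively similar"; if they differ in direction, year 4 may be dropped. Both are optional.

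Protocol 10.1 used two steps: a paired t-test of each year's change against zero, and a one-way ANOVA to "be used to compare these differences to each other, with protected individual linear contrasts performed if" the F-test was significant. SAP section 9 says the analyses now use "repeated measures mixed models rather than the paired t-tests, ANOVA, and ANCOVA analyses as stated in the protocol".

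**The concern.** Protected LSD holds the familywise error near 5% with three levels. It does not with four. After rejection, the only safeguard is that the overall test rejected, and here that test includes baseline. The trial expects a change from baseline, so a drug effect that is identical at years 1, 2 and 4 can open the gate, and the three between-year contrasts then run at a plain 0.05 each.

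Those contrasts bear on a question the protocol's Introduction leaves open: whether the early skeletal response lasts or subsides. A reader who meets the promise of adjustment in SAP 7.4, and then the word corrected in 7.4.1, would take a between-year p-value below 0.05 as adjusted within its endpoint. In a four-level analysis it is not.

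**Working it through.** **Inputs.** Two-sided 0.05 (protocol 10.1; SAP 7.4 gives 0.05). SD of change 7, pilot one-year change 22, clinically meaningful change 10, 8 per arm (protocol 10.2). Eight new subjects gave an on-treatment biopsy (SAP section 9). The documents do not give the split by year or the Cohort 2 count, so 5/4/3 and 3/3/2 are assumptions. Pilot effects are given for two turnover measures only; a change of 4 is added as a weak-effect case.

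**1. Reproduce the plan's own figures.**
- F-test among years, changes 10/15/21, 8 per arm: λ = 8 × [(10 − 15.33)² + (15 − 15.33)² + (21 − 15.33)²] / 49 = 8 × 60.67 / 49 = 9.90. Noncentral F on 2 and 21 df gives 74.8% (stated: 75%).
- Paired t-test, n = 8: noncentrality (10/7) × √8 = 4.04 on 7 df gives 93.1% (stated: 93%).

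**2. Write out the SAP rule.** Four levels give 4 × 3 / 2 = 6 contrasts: three against baseline and three between years. If the 3-df overall test has p < 0.05, each contrast is tested at 0.05. Otherwise each is tested at 0.05/6 = 0.0083.

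**3. Exact value when the gate is open.** Three equal groups compared at 0.05 each: P(q₃,₂₁ > √2 × t₀.₉₇₅,₂₁) = 11.8% from the studentized range (12.2% at large df).

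**4. Simulate the whole rule.** Change-score form, pooled variance, 200,000 runs per case, equal true change at all three years. Chance of at least one false between-year finding:

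| Split (years 1/2/4) | change 4 | change 10 | change 22 |
|---|---|---|---|
| 8/8/8 (planned) | 10.7% | 11.9% | 11.8% |
| 5/4/3 (assumed) | 8.2% | 11.3% | 11.2% |
| 3/3/2 (assumed) | 6.8% | 10.5% | 10.6% |

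A repeat run agreed within 0.2 points. At 8/8/8 the overall test rejects in at least 99.99% of runs for a change of 10 or 22.

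**5. Where the rule does hold.** No effect anywhere, any of six contrasts: 5.0–5.1%. Combining years 2 and 4 when they share a direction, and otherwise dropping year 4: 4.6–5.1%.

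**6. A fading effect.** Years 1 and 2 equal (10 or 22) and year 4 back at baseline: error over the two true nulls (year 1 v 2, year 4 v baseline) is 8.8–9.7%.

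**7. Compare with the protocol's rule.** With equal changes, its ANOVA gate keeps between-year error at about 5%. But its three paired t-tests, in separate subjects, have no stated adjustment: with no effect anywhere, 1 − 0.95³ = 14.3%, against 5.0–5.1% for any of six contrasts under the SAP.

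**8. SAP 7.4.2.4.** Assume baseline equals follow-up, 6-month equals end of therapy, n = 12, 19 or 25, correlation 0.3 or 0.7 (60,000 runs). Four time-points give 9.6–9.8% for a shift of 1–2 SD and 7.3–9.6% for 0.5 SD. The three time-points in section 10 give 4.2–5.2%.

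**9. Check in a mixed model.** REML with compound symmetry, correlation 0.5 and no baseline-value covariate gives 12.5–14.7% under the SAP rule for a change of 10 or 22; single contrasts there run at about 5–7% because the df are approximate. With the SAP's baseline-value covariate added, single between-year contrasts run at 14–18% before any multiplicity. That comes from using baseline as both outcome and covariate; it is a separate matter and is not charged to LSD here.

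**The case against.** The strongest reply is about reach. Both routes that SAP 7.4.1 describes end in three levels, where the rule works, and section 9 names combining years 2 and 4 as the response to early termination. In simulation the shared-direction condition is met in 97–100% of runs for a change of 10 or 22, and 70–90% for a change of 4. This stands as a limit: the documents do not support saying that the primary analysis will carry 11–12% error. The point survives because both routes are optional. In 7.4.2.3 the conditions also leave a gap: pooling needs similar effect sizes and variances, dropping needs qualitative difference, and years 2 and 4 with the same direction but different sizes meet neither.

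A reader might also infer that the SAP quietly removed protection the protocol had. The documents do not support that. Section 9 states that the ANOVA was replaced, though not that it served as a gate. The protocol left its baseline tests unadjusted, so the SAP rule is better with no effect anywhere and worse with equal changes at all years.

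A statistician will know what naming protected LSD implies, and the contrasts are labelled post hoc. This lowers the stakes but does not make the description accurate. Finally, the 7.4.2.4 figure needs two exact equalities at once, which is a narrow case.

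**Conclusion.** The concern holds in a conditional form. In any four-level analysis under SAP 7.4.1, 7.4.2.3 or 7.4.2.4, the contrasts are not corrected once the overall test rejects. For equal changes of 10 or 22, the chance of at least one false between-year finding is about 11–12% per endpoint; for a change of 4 it is about 7–11%. It is about 5% with three levels, so protected LSD is adequate there, and 7.4.2.5, with three time-points, is unaffected.

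These figures rest on normal change scores with SD 7, complete data and assumed year splits. The SAP's time-delay covariate is not modelled, and effect sizes for endpoints without pilot data are assumptions.

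It would go too far to say the plan must add a stricter procedure. A 2-df test among on-treatment years brings between-year error to 4.4–5.0% in change-score form, but to 5.2–7.5% in the mixed-model check. It leaves 8.2–9.7% in the fading pattern and costs power in a study the SAP itself calls under-powered.

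**What to change.** **Required, wording only:**
1. In SAP 7.4.1, 7.4.2.3 and 7.4.2.4, state that in a four-level analysis each contrast is tested at 0.05 without adjustment once the overall test is significant. Do not describe or report those contrasts as corrected or controlled. Keep protected LSD for three-level analyses.
2. Make 7.4.2.4 (four experimental time-points) and section 10 (three) agree.

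**Options for the sponsor, each with a power cost:**
- A 2-df test of equality of years 1, 2 and 4 before the between-year contrasts. It protects that family only, so item 1 is still needed. Contrasts with baseline are unaffected. Power for year 1 v year 4 at changes 10/15/21 falls from 85% to 74% at 8/8/8, from 48% to 34% at assumed 5/4/3, and from 29% to 18% at assumed 3/3/2.
- Holm over all six contrasts. It protects every pattern in the change-score setting, but cuts power for a baseline contrast (change 10, arm of 3, assumed 3/3/2) from 46% to 19%.

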7.4.2 Secondary Efficacy Analyses

7.4.2.1 Covariate adjustments for dose on the primary efficacy analysis models of the bone biopsy endpoints

The bone biopsy repeated measures analyses described in the primary analyses will be explored further by repeating the same analysis but with hPTH dose as an additional covariate. Four measures of dose will be tested as covariates: 1) average dose over the last 6 months prior to the bone biopsy or weaning whichever comes earlier; 2) average dose per kg body weight over the last 6 months prior to the bone biopsy or weaning whichever comes earlier; 3) total daily dose across the whole study up to the time of the bone biopsy or weaning whichever comes earlier; and, 4) total dose per kg of body weight across the whole study up to the time of the bone biopsy or weaning whichever comes earlier. The effects of these dose measures on the bone biopsy results will be modeled separately fitting both linear and quadratic (curvilinear) effects for the dose variable. The best covariate models will be selected based upon examination of the residuals and comparison of the Schwarz-Bayesian criterion.

The relationships between dose and bone biopsy endpoint will be graphically illustrated using scatterplots of the bone biopsy endpoint over dose with appropriate regression lines.

7.4.2.2 Sensitivity analyses of female menopause status in the primary bone biopsy efficacy models

Sensitivity analyses will be performed to test the effects menopause status in females on our best primary efficacy bone biopsy repeated measures models (with or without dose covariates, sections 7.4.1 and 7.4.2.1). Menopause status will be tested as a covariate in the statistical models (excluding males). The covariate for menopausal status will be parameterized into a categorical variable with 2 levels: 1) pre-menopausal female; and 2) menopausal or post-

menopausal female. If the data is rich enough, further exploratory analyses may test for interactions between dose, and menopausal status. Best models will be selected based upon residual analysis and the Schwarz-Bayesian criterion. Results will be summarized in tables.

7.4.2.3 Changes in bone mineralization density based on back-scattered electron imaging of bone-biopsies

Parameters derived from the back-scattered electron imaging of the bone biopsies include the spectral calcium mean, peak, width, low, and high. These spectral calcium parameters will be analyzed separately using repeated measures mixed models with the spectral calcium parameter as the dependent variable, the baseline value of the biopsy endpoint and study cohort as covariates, biopsy time (baseline, 1 year, 2 year, and 4 year) as the repeated measure, and subject as the random variable. Because there are only a few subjects with the 4 year biopsy, the 2 and 4 year biopsies may be collapsed into one biopsy group for analysis purposes if the 2 and 4 year biopsies appear to have similar effect sizes and variances. If the 2- and 4-year biopsies are qualitatively different then the 4-year biopsy endpoints may be dropped from the analysis due to their small sample sizes. Pairwise contrasts will be performed within the repeated measures analyses to compare the effects of the biopsy times on the bone biopsy endpoints.

Since these spectral calcium parameters are secondary endpoints, these analyses are considered more exploratory and thus no adjustments will be made for performing multiple secondary analyses. However, post hoc pairwise comparisons within each repeated measures analysis will be controlled for multiple comparisons using Fisher's protected LSD followed by Bonferroni correction if the overall effect is not significant.

Results will be summarized in a table. The effects of hPTH treatment on the spectral calcium endpoint will be illustrated in figures of the mean \pm se (or geometric means with 95% confidence limits) over biopsy time.

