405 calcium levels within the target range, subjects will be instructed to obtain blood work a minimum of
406 once a month (\pm 1 week). Urine collections should be obtained approximately every 3 months (\pm 2
407 weeks). Additional outpatient blood or urine tests may be ordered as clinically indicated. Participants will
408 be instructed to have lab results sent to the research team. The principal investigator or designee will
409 review the results of these tests, adjust medication doses, and order additional testing according to the
410 HPTH dosing algorithm (Appendix 24.10). Prior to making any dose adjustment decision, the investigator
411 will assess the subject's adherence to medication instructions. The investigator will record all dosing
412 decisions, along with the laboratory values associated with those decisions.

413 **4.5.5 *Monitoring of Calcium-Citrate Ratio and Concomitant Potassium Citrate***

414 All subjects will be monitored for hypocitraturia during the inpatient visits. As hypocitraturia may
415 increase the risk of renal calcifications, subjects with a urinary calcium/citrate ratio greater than 0.7 will
416 receive potassium citrate supplementation, in attempt to lower this ratio. It should be noted that complete
417 normalization of the urinary citrate excretion and reduction of the calcium/citrate may be impossible in
418 these subjects, due to chronic renal tubular dysfunction associated with this disease. Urinary citrate and
419 pH will be monitored on the outpatient collection, as well as during the NIH visits, in subjects treated
420 with potassium citrate. If the urinary pH rises above 7, adjustments to potassium citrate dosing may be
421 made after consultation with the nephrologist on the study team.

422

423 **4.5.6 *Bone Biopsy Procedures***

424 Two percutaneous transiliac crest biopsies will be performed after antibiotic labeling, with one biopsy
425 performed prior to HPTH therapy and the second during HPTH therapy. The biopsy will be performed by
426 a licensed practitioner credentialed in this procedure in the operating room of the NIH Clinical Center
427 under local anesthesia with sedation. The baseline and second biopsy will be obtained from opposite
428 sides. Subjects will be pre-treated with either tetracycline or demeclocycline. Tetracycline will be
429 delivered according to the following schedule: 3 days of tetracycline (250 mg 4 times per day), 12 days

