4. ANALYSIS POPULATIONS

There are 3 Study Cohorts for purposes of analysis:

Cohort 1: subjects who received hPTH under the original protocol;

Cohort 2: subjects who received conventional care in the original protocol and who re-enrolled into the current protocol and who were treated with hPTH;

Cohort 3: new subjects who initially enrolled into the current protocol.

Subjects in cohort 1 will be analyzed separately from the other subjects; only safety analyses will be conducted on this cohort. Subjects in cohorts 2 and 3 will be combined, and efficacy and safety analyses will be conducted on this group. However, the timing of the baseline biopsy relative to the on-treatment biopsy differs in cohorts 2 and 3. For cohort 2 there was a much longer period of time between the baseline biopsy and their 1, 2, or 4 year on hPTH biopsy, in that the baseline period also include their entire period being on conventional care. Whereas for cohort 3, baseline biopsies were taken immediately prior to beginning hPTH. Because of this difference, all efficacy analyses will be repeated on subjects in cohort 3 alone.

Safety Population: The Safety Population will consist of all enrolled subjects (all cohorts) who have started any study treatment including, but not limited to, conventional care. This population will be used for safety data summaries.

Bone Biopsy Population: The Bone Biopsy Population will consist of all subjects who have completed both their baseline and randomized 1, 2, or 4 year bone biopsies. This will include subjects from cohorts 2 and 3.

Secondary Efficacy Population: This population consists of all subjects who received at least one dose of hPTH and had at least one post-baseline non-biopsy efficacy assessment. This will include subjects from cohorts 2 and 3.

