7.2 Efficacy Analysis

7.2.1 Primary Study Endpoints

The primary endpoints are changes in static and dynamic bone histomorphometry after 1 year, 2 years, and 4 years of hPTH therapy. These changes will be determined from antibiotic-labeled biopsies taken before and during hPTH therapy. The original protocol called for analyzing 7 bone markers of static and dynamic bone histomorphometry but the SAP has changed these to 8 bone markers of bone structure and bone remodeling. Analyses will be done on z-scores, when normative data are available. These are listed as follows:

7.2.1.1 *Bone Structure*

1. Cn.BV/TV: cancellous bone volume
2. Ct.Po.N: total number of cortical porosity per mm²

7.2.1.2 *Cancellous Bone Remodeling*

1. Cn.BFR/BS: Cancellous bone formation rate
2. Cn.MS/BS: Cancellous mineralizing surface (bone surface based)

7.2.1.3 *Endocortical Bone Remodeling*

1. Ec.BFR/BS: Endocortical bone formation rate
2. Ec.MS/BS: Endocortical mineralizing surface (bone surface based)

7.2.1.4 *Intracortical Bone Remodeling*

1. Ic.BFR/BS: Intracortical bone formation rate
2. Ic.MS/BS: Intracortical mineralizing surface (bone surface based)

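### The SAP's dose covariates provide for a second biopsy after hPTH weaning began, but no rule excludes or flags such a biopsy in the primary analysis

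*SAP*

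**What the plan says.** - SAP 7.4.2.1 explores dose by "repeating the same analysis but with hPTH dose as an additional covariate". Of the four dose measures, the first is the "average dose over the last 6 months prior to the bone biopsy or weaning whichever comes earlier". The same cut-off ends the other three.
- SAP 7.4: "All efficacy analyses related to the bone biopsies will be performed on the Bone Biopsy Population". SAP 4 defines that population as "all subjects who have completed both their baseline and randomized 1, 2, or 4 year bone biopsies", drawn from cohorts 2 and 3. It sets no condition that weaning had not yet started.
- SAP 7.4.1 enters "biopsy time (baseline, 1 year, 2 year, and 4 year) as the repeated measure". The other terms are the baseline value, cohort, and a covariate for the delay after Cohort 2's baseline biopsy. There is no term, exclusion or sensitivity analysis for weaning.
- Other text puts the second biopsy on drug. SAP 7.2.1 bases the primary endpoints on "antibiotic-labeled biopsies taken before and during hPTH therapy". Protocol 4.5.6 has the first biopsy "performed prior to HPTH therapy and the second during HPTH therapy". SAP 9 calls the 8 new-subject biopsies on-treatment. SAP 7.4.2.5 places the end of hPTH treatment at the point just before weaning.
- SAP 9 reports that when new enrollment closed in June 2015, "subjects began to be slowly weaned off of hPTH".

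**The concern.** The dose analysis has a cut-off for the case where weaning comes before the biopsy. The population and the primary model have no rule for that case. Such a biopsy would therefore count as a 1-, 2- or 4-year hPTH biopsy by default.

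Six of the eight primary endpoints in SAP 7.2.1 are bone formation rate or mineralizing surface, in three bone compartments. They are read from two antibiotic labels given on days 1-3 and 16-18, with the biopsy on day 23 (Protocol Appendix 24.12). They therefore reflect exposure over roughly three weeks, and during a taper that exposure could be reduced. The likely direction is towards baseline. The package insert in Protocol Appendix 24.13 (its section 12.2) reports that a serum formation marker moved back towards its pre-treatment level once treatment stopped, although in osteoporosis patients. Whether raised turnover lasts or fades is the question that the Protocol Introduction leaves open.

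Two features of the SAP would not protect against this. The dose covariate would pair the pre-weaning dose with a biopsy labelled on less drug, so it could not adjust for the lower exposure. And SAP 7.4.1 allows years 2 and 4 to be pooled if their effects merely point the same way, which a diluted effect could still do.

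**Working it through.** **1. The provisions side by side**

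| Provision | What it does with a second biopsy after weaning starts |
|---|---|
| SAP 7.4.2.1, dose covariates | Provides for it: dose is counted only up to weaning |
| SAP 4, Bone Biopsy Population | Admits it, if both biopsies are complete |
| SAP 7.4.1, primary model | Codes it by nominal year; no weaning term |
| SAP 7.2.1 and Protocol 4.5.6 | Outside the description: the biopsy is during therapy |
| SAP 7.4.2.5 | Treatment has already ended by its time-point definition |

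The dose model uses the same biopsies as the primary model. If all of them preceded weaning, the cut-off would always be the biopsy date and the weaning clause would do nothing there.

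**2. The plan's own figures reproduce**

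Inputs from Protocol 10.2: pilot 1-year change in mineralizing perimeter 22 (SD 7) points, meaningful change 10, 8 subjects per arm, two-sided 0.05.

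- Paired t-test: noncentrality (10/7) x sqrt(8) = 4.04 with 7 df gives power 93.1% (stated 93%).
- Between-arm F-test, changes 10, 15 and 21: noncentrality 8 x 60.67/49 = 9.9 with 2 and 21 df gives 74.8% (stated 75%).

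**3. Illustrative shift in an arm mean**

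The documents give neither the number of affected biopsies nor the response lost. Assume one of n biopsies in an arm is affected and has lost a share r of a 22-point change. Shift = 22 x r / n.

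| n | r = 50% | r = 100% |
|---|---|---|
| 2 | 22 x 0.5 / 2 = 5.5 | 22 / 2 = 11.0 |
| 3 | 22 x 0.5 / 3 = 3.7 | 22 / 3 = 7.3 |
| 4 | 22 x 0.5 / 4 = 2.8 | 22 / 4 = 5.5 |

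With no affected biopsy the shift is 0. The protocol's meaningful change is 10 points.

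**4. Illustrative chance of a false difference between times**

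The true change is 22 in both groups, SD 7. Some biopsies in the later group are affected, and the groups are compared by a two-sample t-test at 0.05 (40,000 simulated trials). This is simpler than the SAP's mixed model.

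| Groups | Affected in later group | r = 25% | r = 50% | r = 100% |
|---|---|---|---|---|
| 8 v 8 | 2 of 8 | 5.9% | 7.6% | 9.4% |
| 8 v 8 | 4 of 8 | 9.8% | 21% | 45% |
| 4 v 4 | 1 of 4 | 5.0% | 4.8% | 3.2% |
| 4 v 4 | 2 of 4 | 6.7% | 9.1% | 10.9% |

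Four per group is close to the 8 new-subject biopsies in SAP 9. At that size the harm is mainly a biased estimate, not a false significant test.

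**The case against.** The strongest reply is that the weaning clause is only a precaution. No passage says that any second biopsy followed weaning. SAP 7.2.1, SAP 9 and Protocol 4.5.6 all describe the biopsy as taken on drug, and the Protocol's Schedule of Events places it only at months 12, 24 and 48, at visits marked for PTH therapy. The shortfall in biopsies fits biopsies never obtained at least as well as biopsies obtained during a taper. The clause may also serve SAP 7.4.2.4, which carries dose into the non-biopsy models if it improves the biopsy fits. Those models include subjects without a second biopsy, for whom weaning is the only usable cut-off.

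Most of this stands. A reader might infer that the SAP expects post-weaning biopsies and has decided to count them. The documents do not support that: the expectation rests on one repeated clause, and the counting follows from a missing rule. The explanation through SAP 7.4.2.4 is incomplete, however. It does not explain why the cut-off sits in the biopsy models, and it fits poorly for a subject biopsied at year 1 and treated for longer, whose end-of-therapy outcome would carry a year-1 dose.

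The reply does not supply the missing rule. The on-drug descriptions are not built into the population definition. SAP 7.4.2.4 does recognise that some subjects were off hPTH in later months and rebuilds the non-biopsy time-points for that reason; the biopsy endpoints get no equivalent.

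**Conclusion.** The gap is real. Followed as written, the SAP would analyse a biopsy taken after weaning began under its nominal year and with a pre-weaning dose, at odds with its own endpoint definition. Whether this affects any result is unknown.

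If such a biopsy exists, the formation endpoints in its arm would probably be pulled towards baseline. The figure of 2.8 to 11 points out of 22 is an illustration. It assumes one affected biopsy among 2 to 4, a loss of 50-100% of the response, and the pilot change in raw mineralizing perimeter. The SAP analyses z-scores where norms exist, Cohort 2 adds biopsies beyond the 8, and year 4 may be pooled or dropped, so the actual effect would differ.

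A reader might go further and infer a false return to baseline over time, with the longer arms hit hardest. The documents do not establish this. Trial-wide weaning followed a calendar date, so a recent enrollee's 1-year biopsy could be affected as easily as an older subject's 4-year one. Without enrollment, biopsy and weaning dates, the arm affected cannot be identified.

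This is a cheap improvement worth making, not a fault that must be fixed before the analysis can be relied on.

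**What to change.** - In SAP 4, limit the primary Bone Biopsy Population to subjects whose second biopsy was both labelled and taken before their weaning began.
- Report how many second biopsies fall later, and list each with days since weaning started and the dose at labelling. If there are none, one sentence settles the point.
- Repeat the primary analysis once with the later biopsies included. In that run, compute dose up to the biopsy itself. Within the restricted population the cut-off in 7.4.2.1 is always the biopsy date, so the dose change matters only here.
- Reconcile SAP 4, 7.2.1, 7.4.2.1, 7.4.2.5 and 9 on what counts as a biopsy on hPTH.

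The cost is a few lines of SAP text and one date-based flag. Protocol 4.5.4 already requires dosing decisions to be recorded, and SAP 7.4.2.5 already plans figures of PTH dose through weaning. The downside is that a few biopsies may move from an already small primary set to the sensitivity analysis.
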